After receiving a prescription via remote asynchronous telemedicine, the patient is randomized to either an immediate or delayed treatment arm, and delivery of the Fisher Wallace device will be made by UPS/Fedex/UPS. Upon delivery (as identified by shipment tracking code), individuals will be presented with video how-to instructions, and treatment overviews (along with some device usage troubleshooting facts). The device packaging will also include instructions. A PDF version of the instructions, along with FAQs will be made available via ProofPilot for quick reference.

Participants will be directed to use the device twice per day for 20 minutes, once soon after waking up, and the second time per day 20 minutes prior to attempting sleep.

The study timeline will commence upon completion of the first treatment as identified by the participant in ProofPilot.

Participants who have questions about the device will be referred to ProofPilot customer support. All queries will be logged and reported at the end of the study. ProofPilot will refer those questions that can not be answered with an automated frequently asked questions system to PI [name] and/or the manufacturer (Fisher Wallace) for follow-up.

Primary Outcome Measures:

- Change in Beck Depression Inventory Score in “Treatment week 4” versus Baseline in immediate versus delayed arm.

Secondary Outcome Measures:

- Change in Hamilton Depression Rating Scale from Baseline to “Treatment week 4” in immediate versus delayed arm.
- Change in Beck Depression Inventory Score in “Treatment week 2” versus Baseline in immediate versus delayed arm.
- Change in Patient Health Questionnaire - 8 (PHQ-8) score at “Treatment week 4” versus Baseline in immediate versus delayed treatment arm.
- Change in Patient Health Questionnaire - 8 (PHQ-8) score at “Treatment week 2” versus Baseline in immediate versus delayed treatment arm
- Change in Beck Depression Inventory Score from “Treatment Week 4” to “Treatment week 8” in delayed treatment arm (once they have started use of the actual device).
- Device safety, tolerability and adherence over 8 week period as measured by SAFTEE

Sample Size:

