- Fisher Wallace email marketing to patients who have not purchased a Fisher Wallace device and to providers who may refer patients to the study
- Digital advertising on GoodRx, Facebook, Instagram, Google and other common advertising platforms
- Physician referrals.

All potentially interested participants will be directed to the ProofPilot study recruitment page for registration and screening to begin the study.

Study Design/Methods

All participants upon expressing interest, will be asked to create an account on ProofPilot, and answer some basic demographic questions. (Birthdate, location, sex, timezone, preferred language).

All study activities, except those with the Fisher Wallace device itself, will be completed on ProofPilot. ProofPilot is available across any internet connected device with a reasonable screen size. No download is required.

At enrollment, the participant will be asked a series of screening questions, will complete the PHQ-8, the Beck Depression Inventory and a self administered version of the MINI.

Eligible individuals who will be self consented online, will then be asked to take a photograph with their mobile device of a government issued ID for identification. Participants will set an appointment on ProofPilot with a licensed telemedicine psychiatrist in their state within the next several days.

At that virtual visit, the physician will review the participant's responses to the MINI, and add several additional elements that require a physician assessment. Then the physician will administer the HAM-D - and make a final determination if the participant is a good for the study and authorize a prescription for the device.

Participants will then complete additional baseline measures including the QIDS-SR, PROMIS Sleep Disturbance, and Jenkins Sleep Scale. They will then enter in shipping information to place an order for the Fisher Wallace Device.

All participants will be randomized, with a 50/50 chance, into a control arm or active treatment arm. Control arm participants will receive an active treatment device at the end of week 4. This is a double blind design, the participants, nor any study staff, except those conducting fulfillment are aware of which arm the participant is in until unblinding at the end of the study.

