Eligible individuals will then be asked to take a photograph with their mobile device of a government issued ID for identification. They will then enter in shipping information to place an order for the Fisher Wallace Device.

Participants will then complete additional baseline measures including the QIDS-SR, PROMIS Sleep Disturbance, and Jenkins Sleep Scale.

Meanwhile, collected data from PHQ-8, and the Beck Depression Inventory along with proof of identification will be reviewed by medical oversight licensed in the state in which the participant resides and the order released with a prescription for the device. An appointment will be made for the physician to meet with the patient over video telemedicine. During this visit, the physician will evaluate the patient using previously collected baseline data, and their own assessments (MINI, HAM-D) to ensure proper diagnosis and set a professional assessment baseline.

Should the physician feel the participant is a good match, they will issue the prescription for the Fisher Wallace device.

Shipments will be fulfilled by the sponsor's fulfillment capacity by individuals who are not affiliated with the study. All study staff, including remote physicians, will be blinded to who receives the sham and who receives the active device. Tracking information from UPS/Fedex/USPS will trigger tasks based on where the shipment is in the fulfillment process, including at delivery.

At delivery, ProofPilot will automatically trigger instruction tasks, a treatment expectancy survey, and a notification to "Start the trial." The "Start the trial" task will trigger the 2 week, 4 week and 8 week follow up points key to the outcome measures. It will also trigger the window period for the final (week 4) participant/physician video teleconference assessment.

Participants will receive a daily treatment diary at 6:45AM (though they may complete it anytime within an 18 hour period). The daily treatment diary will ask about treatment adherence and any adverse events from the prior day and provide a morning treatment reminder. Participants will also receive an evening

treatment reminder at 7:15PM. Reminders will be presented from ProofPilot in the morning and in the evening adjusted for the participant timezone.

At the end of the study, participants will need to return both the active and sham devices to qualify for compensation.

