At the 2 week, 4 week and 8 week (unless otherwise noted) time point from “Start of Trial” participants will repeat baseline measures:

- **PHQ-8:** Covers the DSM-IV criteria for major depressive disorder with a discriminant validity of .89 to .92^{1,2}
- **Beck Depression Inventory:** 21-question multiple-choice self-report inventory, one of the most widely used psychometric tests for measuring the severity of depression.
- **MINI:** The M.I.N.I. was designed as a brief structured interview for the major Axis I psychiatric disorders in DSM-IV and ICD-10. Validation and reliability studies have been done comparing the M.I.N.I. to the SCID-P for DSM-III-R and the CIDI (a structured interview developed by the World Health Organization for lay interviewers for ICD-10). The results of these studies show that the M.I.N.I. has acceptably high validation and reliability scores, but can be administered in a much shorter period of time (mean 18.7 ± 11.6 minutes, median 15 minutes) than the above referenced instruments. It can be used by clinicians, after a brief training session. Lay interviewers require more extensive training. The MINI is used in a participant self-administered format, and will be reviewed during a telemedicine visit with a licensed physician to help diagnose major depressive disorder and rule out other mental health disorders.
- **Hamilton Rating Scale for Depression (HAM-D)** (at baseline and 4 week point only): Used by physicians to rate the severity of participant's depression symptoms.
- **QIDS-SR (Quick Inventory of Depression Symptoms):** Nine DSM-IV-TR criterion symptom domains are evaluated to diagnose major depressive disorder (MDD). The Quick Inventory of Depressive Symptomatology (QIDS) provides an efficient assessment of these domains. We are using the Self Report version.
- **Jenkins Sleep Scale** (30 day measure so will skip week 2). Designed as an efficient and brief instrument for use in research, the four-item question evaluates the frequency and intensity of certain sleep difficulties in respondents. With only four items, it cannot begin to address the entire spectrum of sleep disorders and should only be considered for use as a preliminary screening device, and is therefore used in conjunction with PROMIS Sleep Disturbance.

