- **Promis Sleep Disturbance:** The PROMIS-SD had greater measurement precision than the Pittsburgh Sleep Quality Index (PSQI) and the Epworth Sleepiness Scale (ESS) as indicated by larger test information values across the continuum of severity, despite having fewer total items, a major advantage for both research and clinical settings.³
- **COMBINE SAFTEE** (systematic assessment for treatment of emergent events modified for mental health and substance abuse)

The blue bar indicates shipment/delivery of the active or sham device.

¹ Kroenke, Kurt; Spitzer, Robert L; Williams, Janet B W (2017-05-31). "The PHQ-9". Journal of General Internal Medicine. 16 (9): 606–613. doi:10.1046/j.1525-1497.2001.016009606.x. ISSN 0884-8734. PMC 1495268. PMID 11556941

² Löwe, Burnd; Spitzer; Gräfe; Kroenke; Quenter; Zipfel; Buchholz; Witte; Herzog (February 2004). "Comparative validity of three screening questionnaires for DSM-IV depressive disorders and physicians' diagnoses". Journal of Affective Disorders. 78 (2): 131–140. doi:10.1016/s0165-0327(02)00237-9. PMID 14706723.

³ A. John Rush, Ira H. Bernstein Development of short forms from the PROMISTM sleep disturbance and Sleep-Related Impairment item banks, Behav Sleep Med. 2011 Dec 28; 10(1): 6–24. doi: 10.1080/15402002.2012.636266 PMCID: PMC3261577 NIHMSID: NIHMS335121 PMID: 22250775

	Enroll	Baseline		2-Week	4-Week	8 Week
Inclusion/Exclusion	X					
Consent						
PHQ-8	X			X	X	X
Beck Depression Inventory	X			X	X	X
M.I.N.I Screen	X					
HAM-D	X				X	
Physician Telemedicine Visit	X				X	
Randomization	X					
Treatment Expectancy			X			
Instructions			X			
Quick Inventory of Depressive Symptomatology (QIDS-SR)		X		X	X	X
Jenkins Sleep Scale		X			X	X
Promis Sleep Disturbance		X		X	X	X
COMBINE SAFTEE				X	X	X
Final Feedback & Tolerability						X
Daily treatment adherence and adverse events						

Adverse Event Reporting & Medical Oversight

Licensed medical providers in the state in which the participant lives will provide medical oversight for this effort.

Adverse events will be collected qualitatively via customer support in the ProofPilot platform. In addition, medical oversight staff will automatically receive alerts if participants have a PHQ-8 score over 20 at the 2 week, 4 week or 8 week point. Those participants will also receive notifications to contact local medical support.

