Participants will complete the COMBINE SAFTEE at the 2 week, 4 week and 8 week mark to provide additional data for safety and tolerability not otherwise collected.

All adverse events will be followed up upon and tracked in ProofPilot.

Participant Compensation

Participants may earn up to \$100 for participation in the study.

- \$10 Visa Gift Card for Baseline through completing first Fisher Wallace Treatment (aka 'Start Task') as identified above..
- \$90 presented within 2 weeks of study completion (as defined by return of both the active and shame devices) based on the following:
 - \$20 for each 2 week check in (up to \$60)
 - Up to \$30 as calculated by percentage of daily diaries completed over the 8 weeks

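### COMBINE SAFTEE is not scheduled before the device is used, so complaints that predate treatment are hard to separate from emergent ones; one online baseline form would close the gap.

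*Protocol*

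**What the plan says.** The secondary outcomes include "Device safety, tolerability and adherence over 8 week period as measured by SAFTEE", so SAFTEE is the named instrument for safety and tolerability. The Study Design/Methods section describes it as a "systematic assessment for treatment of emergent events modified for mental health and substance abuse".

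Three places in the protocol bear on its timing:

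- **Follow-up measures list (Study Design/Methods).** At weeks 2, 4 and 8, "participants will repeat baseline measures", unless an exception is noted. SAFTEE is the last item and carries no exception. The HAM-D and the Jenkins scale each carry one.
- **Schedule table.** The row "COMBINE SAFTEE" is marked at 2-Week, 4-Week and 8 Week. Enroll and Baseline are empty.
- **Adverse Event Reporting & Medical Oversight.** "Participants will complete the COMBINE SAFTEE at the 2 week, 4 week and 8 week mark". This matches the table.

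The steps before the device arrives do not mention SAFTEE. At enrollment participants "will complete the PHQ-8, the Beck Depression Inventory and a self administered version of the MINI". Later they complete "additional baseline measures including the QIDS-SR, PROMIS Sleep Disturbance, and Jenkins Sleep Scale". The physician adds the HAM-D.

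**The concern.** An emergent event is one that is new, or worse, relative to the state before treatment. Deciding that from a symptom form needs either a pre-treatment answer on the same form or wording that asks about onset or change. The first is not scheduled, and the second is not shown.

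Everyone enrolled has major depressive disorder, and the trial itself measures sleep disturbance at baseline, so complaints present before the first session are foreseeable. The first SAFTEE, at week 2, would record them alongside anything the device caused.

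The protocol intends weeks 1-4 to support a premarket submission on safety as well as effectiveness, so the per-arm rates from this instrument matter. The issue is what is collected and when. An analysis plan cannot recover an answer that was never taken.

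**Working it through.** **Step 1: is there any pre-device SAFTEE?** Set side by side, the schedule table (weeks 2, 4, 8), the adverse event section (weeks 2, 4, 8) and the enrollment and baseline steps (no mention) agree that there is none. Only the heading of the follow-up list points the other way.

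**Step 2: what else could stand in for it?**

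| Source | Before the device? | Covers |
|---|---|---|
| PHQ-8, Beck, HAM-D, QIDS-SR | yes | depressive symptoms, including some sleep items |
| PROMIS Sleep Disturbance, Jenkins | yes | sleep |
| Daily diary | no pre-device entry described | prior day's adherence and adverse events |
| SAFTEE | no | safety and tolerability outcome |

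The gap is therefore widest for complaints that are neither mood nor sleep.

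**Step 3: how large could the mixing be?** The protocol states no symptom rates and no planning figure for SAFTEE, so there is nothing of its own to reproduce. Every value below is an assumption:

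- b = share who already have a given symptom that persists: 10% to 40%
- e = share of the others who develop it: 5%, or 20% active versus 5% sham for the arm comparison
- the form records presence or absence only

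Rate shown = b + (1 − b) × e.

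*Single-arm rate, e = 5%:*
- b = 10%: 0.10 + 0.90 × 0.05 = 14.5%; truly emergent share 0.045 / 0.145 = 31%
- b = 40%: 0.40 + 0.60 × 0.05 = 43%; truly emergent share 0.03 / 0.43 = 7%

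*Arm difference, e = 20% versus 5% (15 points among symptom-free participants):*
- b = 10%: active 0.10 + 0.90 × 0.20 = 28%; sham 14.5%; difference 13.5 points
- b = 40%: active 0.40 + 0.60 × 0.20 = 52%; sham 43%; difference 9 points

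**Step 4: is the arm difference biased?** The difference shown is (1 − b) × 15 points. That is also the difference in new cases counted over all randomized participants: 18% − 4.5% = 13.5 points at b = 10%, and 12% − 3% = 9 points at b = 40%. So the comparison is diluted relative to symptom-free participants, but unbiased for the whole randomized group.

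What the background adds is variance. With equal arms, the sum of p(1 − p) over the two arms is:
- b = 10%: 0.2016 + 0.1240 = 0.3256 for all reports, against 0.1476 + 0.0430 = 0.1906 for new cases only; standard error ratio √(0.3256 / 0.1906) = 1.31
- b = 40%: 0.2496 + 0.2451 = 0.4947, against 0.1056 + 0.0291 = 0.1347; ratio √(0.4947 / 0.1347) = 1.92

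**The case against.** The strongest defence has four parts.

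- **The timing is not in real doubt.** The table and the adverse event section agree, and the list heading is loose: the MINI sits in the same list yet is marked only at Enroll. This stands. A reader might infer a firm contradiction, or that a baseline SAFTEE was meant and then lost. The documents do not support that. The mismatch is editorial, and the substantive point is the missing baseline.
- **The form may ask about onset or worsening.** The documents do not reproduce its items and describe it as assessing emergent events. This stands too. A reader might infer that old and new complaints cannot be told apart at all. That would require a pure presence/absence form, which is not shown.
- **Other sources help.** Mood and sleep are measured before the device, and the diary can help date onset after the start: "The daily treatment diary will ask about treatment adherence and any adverse events from the prior day". This narrows the gap without closing it. No diary entry before the device is described, and the protocol says SAFTEE is there to add safety data not collected elsewhere.
- **The sham arm handles background.** Through week 4 randomization balances it, so the difference in symptom rates is unbiased. This stands for the comparison but not for the per-arm rates. It does not extend to weeks 5-8, when both arms are on active devices. The delayed arm's week 4 SAFTEE can serve as a reference before its active device; the immediate arm has none.

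**Conclusion.** The point holds as a cheap improvement to data collection. The named safety and tolerability measure has no pre-device administration, so pre-existing complaints, chiefly those outside mood and sleep, are hard to separate from emergent ones. The likely effects are inflated per-arm emergent rates and a noisier active-versus-sham comparison.

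The figures of 14.5-43% shown against 5% true emergence, and 13.5 to 9 points against 15, rest wholly on assumed rates, full persistence and a presence/absence form. They show direction and plausible scale and are not estimates for this trial. If the form asks about new or worsened events, the effect would be smaller.

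A reader might go further and infer that the randomized safety comparison is biased, or that the trial loses a stated amount of power on safety. Neither follows: the comparison is unbiased through week 4, and the protocol plans no power for SAFTEE. The primary efficacy outcome is unaffected.

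**What to change.** 1. Mark SAFTEE in the Baseline column of the schedule table, completed online with the QIDS-SR and the sleep scales before first device use, and add it to the baseline steps in Study Design/Methods.
2. State that a SAFTEE item counts as emergent only if it is new or worse than at baseline.
3. Reconcile the follow-up measures list, the schedule table and the adverse event section, and correct the MINI entry at the same time.

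If no baseline SAFTEE is added, take it out of the list of repeated baseline measures and state how pre-existing symptoms will be identified.

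The cost is one more form on a platform already in use, a few minutes of extra baseline burden per participant, and no change to the sample size.
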